### **3.0 Study Design**

This is an open-label non-randomized single-institution study for subjects with inoperable, recurrent/refractory advanced hepatocellular carcinoma (HCC). Subjects must have failed or be intolerant of standard first line therapy, sorafenib (Nexavar®). Eligible subjects will receive 125 mg PD-0332991 capsules orally once daily, administered days 1-21 of a 28-day cycle, in repeated cycles.

Subjects will be permitted to receive protocol directed therapy until disease progression by modified RECIST (Version 1.1) (Response Evaluation Criteria in Solid Tumors) guidelines or clinical progression, unacceptable toxicity, withdrawal of consent or death. Tumor response assessment will be performed by the Investigator and will consist of evaluation by CT or MRI using modified RECIST (Version 1.1) guidelines every 8 weeks. Subjects who discontinue therapy for disease progression or other reasons will be followed for safety on Day 28 ( $\pm$  3 days), Day 56 ( $\pm$  3 days) and every 3 months thereafter or until death, from the last administration of protocol –directed therapy.

Subjects will be continuously assessed for evidence of acute and cumulative toxicity. Vital signs, Physical examinations, performance status, laboratory safety tests will be obtained and assessed prior to drug administration and at regular intervals throughout the study. Toxicity will be evaluated every 2 weeks during the first 3 cycles and thereafter monthly (once per cycle) by the Investigator according to National Cancer Institute (NCI) Common Terminology Criteria for Adverse Events (CTCAE), Version 4.0 (which can be viewed on-line at the following NCI web site: <http://ctep.cancer.gov/reporting/ctc.html>).

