### **5.4 Subsequent visits on study – Response and Toxicity Assessment**

Safety and tolerability of the study drug will be assessed every 2 weeks after the initiation of PD-0332991 for the first 3 cycles of treatment, and every 4 weeks thereafter. Procedures will be as described for Visit 3. Additionally, Serum AFP will be monitored every 4 weeks and imaging will occur every 8 weeks after initiation of therapy to determine response of the disease to treatment. Subjects will undergo tumor response assessment per modification of RECIST (Version 1.1) guidelines. Radiological assessments must include CT of the chest, abdomen and pelvis and MRI of the liver. Magnetic Resonance Imaging is the preferred study for imaging the liver and must include T1, T2/flair and diffusion weighted imaging. Studies will be obtained at

baseline and according to schedule of observations until disease progression, death, withdrawal of consent, end of study or start of a new treatment. Unscheduled imaging may be conducted at the discretion of the Investigator.

Adverse events are defined in section 9.0. The investigator is responsible for reviewing all laboratory and clinical data, determining clinical significance and assessment of adverse events. It will be left to the investigator's clinical judgment to determine whether an adverse event is related and of sufficient severity to require subject's removal from treatment or from the study. The subject may also withdraw voluntarily from treatment due to what he/she perceives as an intolerable adverse event. If this arises the subject will be observed with extra visits until symptoms cease or the condition becomes stable. Adverse events will be graded using the National Cancer Institute (NCI) Common Toxicity Terminology Criteria for Adverse Events v 4.0 (CTCAE v 4.0).

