### **5.5 Follow-up Visits**

After disease progression or drug intolerance, subjects will be scheduled for follow-up assessment approximately 30 days after the last administration of protocol specific therapy. At this visit subjects will undergo clinical assessment including: interval history, limited physical examination, weight, vital signs, signs/symptoms, and performance status. AEs and concomitant meds will be obtained. Bloodwork including: CBC, comprehensive metabolic panel, AFP will be collected and recorded. Subjects will be followed every 3 months in clinic to collect information on their general health status and their liver cancer. This visit must include at a minimum interval history, physical exam, concomitant medications and toxicity assessment. If possible other treatments, outcomes and survival should be obtained.

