## **6.2 Response Assessment**

Response is assessed on the basis of clinical, radiological, and pathological criteria. Standard imaging via MRI and/or CT scan will be used for evaluation of nodal disease based on RECIST criteria. These techniques should be performed with cuts of 10 mm or less in slice thickness contiguously. Spiral CT should be performed using a 5 mm contiguous reconstruction algorithm.

The subject's response will be assessed based on the response of the target lesions, the response of non-target lesions and the presence or absence of new lesions through out the course of the study.

Response Criteria for Target Lesions:

Complete Response (CR)	Disappearance of all target lesions
Partial Response (PR)	At least 30% decrease in the sum of the LD of target lesions, taking as reference the baseline sum LD
Progressive Disease (PD)	At least 20% increase in the sum of the LD of target lesions, taking as reference the smallest sum LD recorded since the treatment started or the appearance of one or more new lesions.
Stable Disease (SD)	Neither sufficient shrinkage to qualify for PR nor sufficient increase to qualify for PD, taking as reference the smallest sum LD recorded since the treatment started

Response Criteria for Non-target Lesions

Complete Response (CR)	Disappearance of all non-target lesions and normalization of tumor marker level
Incomplete Response/Stable Disease (SD)	Persistence of one or more non-target lesions and or maintenance of tumor marker above normal limits.
Progressive Disease (PD)	Appearance of one or more new lesions and or unequivocal progression of existing non target lesions

Subjects with global deterioration in health status requiring discontinuation of treatment without objective evidence of disease progression will be classified as having symptomatic deterioration. Every effort will be made to document objective progression.

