### **11.1 Evaluation of Efficacy**

Efficacy endpoints will be estimated for all subjects. The tumor response endpoints will be performed on all subjects. The population will be evaluated on an intent-to-treat analysis defined as subjects who received at least two cycles of study medication and have completed the week 8 response assessments. TTP, ORR will be assessed by standard imaging (MRI and/or CT scans, as appropriate) utilizing modified RECIST (Version 1.1) criteria. Assessments will be performed at screening and after every 2 cycles of treatment (every 8 weeks) thereafter. TTP and overall survival will be evaluated using the Kaplan-Meier method. Median TTP and median survival will be estimated with corresponding 90% confidence intervals. Subjects that are not evaluable will be replaced with subjects with evaluable data.

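### Section 11.1 and the off-treatment visits conflict with the 8-week scan rule in 3.0 and 5.4, leaving it unsettled how time to progression (TTP) is measured after a patient stops drug without progression

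*Combined protocol and SAP*

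**What the plan says.** **Calendar rule.** Section 3.0 calls for "evaluation by CT or MRI using modified RECIST (Version 1.1) guidelines every 8 weeks". Section 5.4 sets the starting point: "imaging will occur every 8 weeks after initiation of therapy to determine response of the disease to treatment". It then says how long imaging lasts: "baseline and according to schedule of observations until disease progression, death, withdrawal of consent, end of study or start of a new treatment". Stopping PD-0332991 is not on that list.

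**Cycle rule.** Section 11.1 says: "Assessments will be performed at screening and after every 2 cycles of treatment (every 8 weeks) thereafter".

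**Off-treatment visits.** Section 3.0 describes the purpose as safety: "Subjects who discontinue therapy for disease progression or other reasons will be followed for safety on Day 28". Section 5.5 covers patients who stop for progression or drug intolerance. Its first visit is a clinical assessment plus blood tests ("Bloodwork including: CBC, comprehensive metabolic panel, AFP will be collected and recorded"). For the 3-monthly visits it says: "This visit must include at a minimum interval history, physical exam, concomitant medications and toxicity assessment". Section 5.7 adds safety and survival information. None of these lists CT or MRI.

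**Leaving before progression.** Sections 5.3, 5.6 and 9.13 take patients off for reasons other than progression: a second Grade 3 or greater toxicity (with listed exceptions), less than half the required dose over two consecutive cycles, noncompliance, or investigator judgement. The wording is removal or withdrawal from the study, not from the drug.

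**When progression is not assessed.** Section 6.2, on symptomatic deterioration, says: "Every effort will be made to document objective progression". Section 7.1 uses the date of last dose or of death as the event date when disease could not be assessed.

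**The concern.** The two clocks agree only if every cycle runs on time and the patient stays on drug until progression. The protocol expects neither. Drug is held for related Grade 3 or greater toxicity (5.3, 9.13), and Table 8.3 foresees a patient unable to resume for a whole cycle.

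One patient could therefore be handled in two ways. Under 5.4, someone who stops for toxicity at week 14 is still scanned at weeks 16, 24 and so on. Under 11.1 and 5.5 that person has no further scheduled scan, and being off the study makes it doubtful that 5.4 still applies. The TTP record would then depend on which section the site followed. People who stop for toxicity or decline are unlikely to be a random subset.

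The two possible errors run in opposite directions. A missing scan combined with the 7.1 rule makes TTP too short. A late scan makes it too long.

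**Working it through.** **1. The plan's own figure.** Inputs from 11.0: median 24 against 12 weeks, alpha 0.05, power 90%, N = 19. For a one-sample exponential test, events = (z_alpha + z_power)² / (ln 2)². One-sided: (1.645 + 1.282)² / 0.480 = 17.8, so 18. That is within 2 of 19. Two-sided gives 22, which does not match. The match therefore needs one-sided alpha and an observed event in essentially every patient. Power at 19 events is Φ(√19 × 0.693 − 1.645) = 91.6%.

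**2. How many patients the gap could touch.** The documents give no stopping rate. Assumptions: exponential TTP with median m weeks, 8-week scans, and a constant 4% or 8% chance per 4-week cycle of stopping for reasons other than progression. Let q = 2^(−8/m) be the chance of no progression in 8 weeks, and r the chance of not stopping in 8 weeks: 0.96² = 0.9216 or 0.92² = 0.8464.

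Counting from the first dose, the share stopping before a scan shows progression is 1 − (1 − q)r/(1 − qr). Section 11.1 analyses only patients with two cycles and the week-8 assessment, and replaces the others. Among patients still on drug at week 8 the share is q(1 − r)/(1 − qr).

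| Median | Stop per cycle | From first dose | Still on drug at week 8 | Of 19 |
|---|---|---|---|---|
| 12 wk (q = 0.630) | 4% | 18.7% | 11.8% | 2.2 |
| 12 wk | 8% | 32.9% | 20.7% | 3.9 |
| 24 wk (q = 0.794) | 4% | 29.2% | 23.2% | 4.4 |
| 24 wk | 8% | 46.8% | 37.1% | 7.1 |

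The last two columns are the relevant ones.

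**3. If those patients are censored at stopping.** Power = Φ(√(19(1 − s)) × 0.693 − 1.645), where s is the share censored and censoring is taken as non-informative.
- s = 10%: 17.1 events, 88.9%
- s = 20%: 15.2 events, 85.5%
- s = 30%: 13.3 events, 81.1%
- s = 37%, the top of the table: 19 × 0.629 = 11.95 events, √11.95 = 3.457, and 3.457 × 0.693 − 1.645 = 0.75, giving about 77%

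**4. If 7.1 makes the last dose the event.** This was simulated with 19 patients, a true median of 24 weeks, 8-week scans and a one-sided exponential test (assumed, since 11.0 and 11.1 name no test). With scans continued, 98% of trials reject. If 10%, 20% or 30% stop without progression and the last dose is counted as the event, this falls to 95%, 86% or 68%. Stopping is counted from the first dose here, so these figures slightly overstate the fall for stopping confined to after week 8.

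**5. If a hold also stops the cycle clock.** With block length L between scans, mean recorded TTP is E[L] / (1 − E[2^(−L/m)]). At m = 12 and L = 8 this is 8/0.370 = 21.62 weeks. A 1-week delay in 20% of two-cycle blocks gives 8.2/0.377 = 21.74, which is 0.1 week more. A 4-week delay in 40% of blocks gives 9.6/0.422 = 22.75, which is 1.1 weeks more. Results at m = 24 are 0.1 and 1.1. Delay frequencies and lengths are assumptions. For one patient who loses a cycle, progression at week 7 would be recorded at week 12 instead of week 8.

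**The case against.** The strongest reply is that the plan already keeps scanning these patients. Section 5.4 names the events that end imaging, and stopping the drug is not one of them. The 5.5 list for the 3-monthly visits is a minimum, 5.4 allows unscheduled imaging, and 5.4 points to a schedule of observations that is not in the text available for review and may list these scans. This much stands: a reader might infer that the protocol plans to stop measuring TTP at drug discontinuation, and the documents do not say that. What remains is that 5.5 and 5.7 itemise the off-treatment visits without imaging, 3.0 describes them as safety follow-up, and patients are said to leave the study.

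A reader might also infer that the gap flatters the drug. The documents do not support that as the main effect. Section 7.1 can turn an unscanned patient into an early event, and it accepts clinical progression as an event without a scan.

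Nor is it settled that held patients are scanned late. Section 11.1 itself adds that two cycles means every 8 weeks and speaks of week-8 assessments. The Treatment Schedule in 5.0 fixes a cycle at 28 days, and Table 8.3 and 5.6 can be read as letting cycles elapse while drug is withheld. The delay instruction in Table 8.3 points the other way. Even if scans do slip, the effect is small beside that of the 8-week grid. In simulation at a true 12-week median, that grid alone gives 24% false positives under the assumed test, and 27% if half the patients have 10-week spacing.

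**Conclusion.** The conflict is real and concerns the primary endpoint; it should be resolved. It is a contradiction to reconcile, not a settled decision to stop scanning.

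If 11.1 and 5.5 govern, about 2 to 4 of 19 evaluable patients at a 12-week median, and 4 to 7 at 24 weeks, would have no scan after stopping. Counting from the first dose would suggest about 4 to 6 and 6 to 9, but many of those stop before week 8 and are replaced under 11.1. The consequence depends on 7.1: a moderate loss of power if these patients are censored, a larger loss if the last dose becomes the event. Late scanning is conditional and secondary, at 0.1 to 1.1 weeks in mean recorded TTP.

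The text of the conflict is certain. The sizes rest on exponential TTP, assumed stopping and delay rates, and an assumed one-sided one-sample test.

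**What to change.** - **11.1:** state that tumor imaging runs every 8 weeks from the first dose, regardless of dose holds, as in 5.4.
- **5.5:** state that subjects off drug without documented progression continue the 5.4 imaging until progression, new anti-cancer treatment, withdrawal of consent or death.
- **7.1:** state that stopping drug without progression is not in itself a TTP event while the 5.4 scans continue.
- **5.3, 5.6 and 9.13:** reconcile the wording about removal from the study with continued imaging under 5.4, without altering any criterion for stopping treatment.

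The sample size of 19 is unaffected, because no input to it changes. The cost is a wording amendment, plus a few off-treatment scans that 5.4 already requires, in some of at most 25 patients.

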### **11.2 Safety Analysis**

The clinical safety data will be summarized using descriptive statistics.

### **12.0 Data Disclosure and Patient Confidentiality**

Patient medical information obtained as a result of this study is considered confidential. Disclosure to third parties other than to the patient's primary physician and to those noted below is prohibited. All reports and communications relating to subjects in this study will identify each patient only by his/her number (and initials if allowed by local regulations). Data generated as a

result of this study must be available for inspection upon request by the FDA (or other Health Authority or government agency), Data Safety Monitoring Board, and the IRB.

Confidentiality will be maintained at all times unless government regulation or applicable law requires disclosure. If local or national regulations are modified to require additional consent(s) or documentation for release of source documents or other medical information, required for the study, it is the responsibility of the investigator to obtain such consent and documentation with relevant approvals by the local IRB.

### **12.1 Data Collection**

The investigator is required to prepare and maintain adequate and accurate case histories designed to record all observations and data pertinent to this investigation for each subject enrolled.

### **12.2 Records Retention**

The Investigator must retain all source documents for the maximum period required by applicable regulations and guidelines, or Institution procedures. If the Investigator withdraws from the study (e.g., relocation, retirement), the records shall be transferred to a mutually agreed upon designee (e.g., another Investigator, IRB). Notice of such transfer will be given in writing to IRB.

### **12.3 Protocol Deviations/Exceptions**

Deviations/exceptions from listed eligibility criteria will not be allowed under any circumstances. An accidental or unintentional deviation from the approved protocol, that in the opinion of the investigator, places one or more subjects at increased risk, or affects the rights or welfare of subjects, must be reported to the IRB and DSMC immediately.

## **13.0 Ethical Considerations**

### **13.1 Protection of Human Subjects from Research Risks**

The study will be conducted in accordance with the Declaration of Helsinki and with rules and regulations in accord with the U.S. Office of Protection from Research Risks (OPRR).

### **13.2 Institutional Review Board**

The study will be reviewed and approved by a duly constituted IRB before patients are screened for entry. The investigator will ensure that all aspects of the IRB review are conducted in accordance with current institutional, local, and national regulations. Amendments to the protocol will be subject to the same requirements as the original protocol. The Investigator will submit all periodic reports and updates that the IRB may require, including any final close out reports. The Investigator will inform the IRB of any reportable adverse events as required by local regulations.

### **13.3 Informed Consent**

Each subject will be provided with oral and written information that describes the nature and duration of the study in a language he/she can understand. The required schedule for treatment and interval safety evaluations (irrespective of holidays), plus the planned follow-up schedule, should be carefully reviewed and possibly reinforced with a calendar. The patient must consent in writing to participate before undergoing therapy on the protocol. The original signed consent form will be retained. Each subject will be given a copy of his/her consent form.

#### **14.0 Data Safety Monitoring Board**

The study Principal Investigator will monitor toxicities monthly, submitting quarterly safety and monitoring reports to the Clinical Research Management Office and The Data Safety Monitoring Committee (DSMC). All unexpected on-site adverse events and serious adverse events (SAEs) are required to be submitted to the TJU IRB and the DSMC within 48 hours. Fatal adverse events which are unexpected must be reported within 24 hours to the TJU IRB and the DSMC. Fatalities not related to the study drug/device must be reported within 5 days.

A medical monitor (a physician or other member of the DSMC who has expertise in the therapeutic area of the protocol and is not directly involved in this trial) will be identified for the protocol. The medical monitor will review all adverse events (in addition to unexpected adverse events), safety data and activity data observed in the ongoing clinical trial.

The PI provides a report to the DSMC of all AE/SAEs, safety and toxicity data, and any corrective action that occurred on a quarterly basis. The medical monitor also provides a summary of their review. The summary of all discussions of adverse events are submitted to the DSMC, and these reports are reviewed during the DSMC meetings that take place quarterly. Patients are only identified by initials, and no other PHI is included in the reports.

The medical monitor may recommend reporting adverse events and relevant safety data not previously reported, and may recommend suspension or termination of the trial based on their review of AE/SAE data observed throughout the life of a clinical trial. In such circumstances, and “ad hoc” DSMC meeting will be called to discuss corrective action with the PI.

The summary of all discussions of adverse events are included in the Kimmel Cancer Center (KCC) investigator’s reports to the TJU IRBs as part of its annual progress report. The DSMC and the TJU IRB may, based on the monitor’s recommendation suspend or terminate the trial. The quarterly safety and monitoring reports include a statement as to whether this data has invoked any stopping criteria in the clinical protocol.

#### **15.0 Audits**

In addition to review by the DSMC, the study will be audited by an independent auditor once 10% of target accrual has been achieved. The study will be re-audited once 50% of target accrual has been achieved. However, a study can be audited at any time based on recommendations by the IRB, DSMC, CCRRC and/or the Director of Clinical Investigations, KCC. Special audits may be recommended by the IRB, DSMC or CCRRC based on prior findings, allegations of scientific misconduct and where significant irregularities are found through quality control procedures. Any irregularities identified as part of this process would result in a full audit of that study.

In addition to the audits at 10 and 50%, the CRMO randomly audits at least 10 percent of all patients entered into therapeutic KCC trials and other trials as necessary, on at least a bi-annual

basis, to verify that there is a signed and dated patient consent form, the patient has met the eligibility criteria, and that SAEs are documented and reported to the TJU IRB.

